### **9.1.2. Secondary Safety and Efficacy Assessments**

- Serious adverse events (SAEs) and treatment-emergent adverse events (TEAEs)
- Rates per 30 days and per subject year of total hypoglycemic events (symptomatic or asymptomatic)
- Incidence and rates per 30 days and per subject-year of nocturnal, severe, documented symptomatic and asymptomatic hypoglycemic events
- Change in HbA1c levels at Weeks 12 and 24 from baseline
- Percentage of subjects reaching HbA1c targets  $\leq 6.5\%$  or  $< 7\%$
- Change in FBG levels at Weeks 4, 8, and 12 from baseline
- Self-monitored 7-point SMBG levels at baseline, Weeks 4, 8, 12, and 24
- Change in 7-point SMBG levels at Weeks 4, 8, 12, and 24 from baseline
- Intrasubject variability, as measured by the standard deviation (SD) of 7-point SMBG levels
- Basal insulin dose (U/day and U/kg/day)
- Change in weight and body mass index at Week 24 from baseline
- Change in Insulin Treatment Satisfaction Questionnaire (ITSQ) score at Week 24 from Week 4

### **9.1.3. Appropriateness of Assessments**

All safety and efficacy assessments included in this study are generally regarded as reliable and accurate with respect to diabetes mellitus.

## **9.2. Adverse Events**

Investigators are responsible for monitoring the safety of subjects who have entered this study and for alerting Lilly or its designee of any event that seems unusual, even if this event may be considered an unanticipated benefit to the subject.

The investigator is responsible for the appropriate medical care of subjects during the study.

Investigators must document their review of each laboratory safety report.

The investigator remains responsible for following, through an appropriate health care option, AEs that

- are serious or otherwise medically important
- are considered related to the investigational product or the study, or
- cause the subject to discontinue the investigational product before completing the study.

The investigator will record all relevant AE/SAE information in the eCRF. The subject should be followed until the event

- resolves
- stabilizes with appropriate diagnostic evaluation, or

- is reasonably explained.

The frequency of any additional follow-up evaluations of AEs between site and telephonic visits is left at the discretion of the investigator.

After the ICF is signed, study site personnel will record the occurrence and nature of each subject's preexisting conditions, including clinically significant signs and symptoms of the disease under treatment in the study in eCRFs. In addition, site personnel will record any change in the condition(s) and any new conditions as AEs. Investigators should record their assessment of the potential relatedness of each AE to protocol procedure and investigational product in the eCRFs.

The investigator will interpret and document whether or not an AE has a reasonable possibility of being related to study treatment, study device, or a study procedure, taking into account the disease, concomitant treatment, or pathologies.

A "reasonable possibility" means that there is a cause and effect relationship between the investigational product, study device, and/or study procedure and the AE.

The investigator answers yes or no when making this assessment.

Planned surgeries and nonsurgical interventions should not be reported as AEs unless the underlying medical condition has worsened during the course of the study.

If a subject's investigational product is discontinued as a result of an AE, study site personnel must report this to Lilly or its designee via eCRFs clarifying, if possible, the circumstances leading to any dosage modifications or discontinuations of treatment.

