### **9.2.1.1. Suspected Unexpected Serious Adverse Reactions**

Suspected unexpected serious adverse reactions (SUSARs) are serious events that are not listed in the Investigator’s Brochure (IB) and that the investigator identifies as related to investigational product or procedure. United States 21 CFR 312.32 and European Union Clinical Trial Directive 2001/20/EC, and the associated detailed guidance or national regulatory requirements in participating countries require the reporting of SUSARs. Lilly has procedures that will be followed for the identification, recording, and expedited reporting of SUSARs that are consistent with global regulations and the associated detailed guidance.

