#### 10.3.2.4. Adverse Events Analyses

Adverse events will be listed by

- subject
- system organ class (SOC)
- Medical Dictionary for Regulatory Activities® preferred term (PT)
- severity, and
- relationship to the study disease, drug, device, or procedure for all subjects.

Adverse events (including injection site reactions and neoplasms) will be summarized as TEAEs for the FAS population. Treatment-emergent AEs are defined as events that are newly reported after the first study drug treatment or are reported to have worsened in severity after the first study drug treatment. The proportion of subjects experiencing each TEAE will be presented by PT, SOC, and treatment group. The proportion of subjects experiencing each TEAE that is assessed as possibly related to the study disease, drug, or procedures will also be summarized. Treatment-emergent AEs will be summarized by PT within SOC and by PT by decreasing frequency.

All SAEs will be listed by subject and summarized by treatment as counts and percentages. Similar analyses will be performed for discontinuations due to AEs.

All AEs analyses will be repeated for the PPS population.

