16.1 Variables and derivations

Adverse Events (AEs) will be coded using MedDRA central coding dictionary, Version (refer to DMP for dictionary version).

Adverse events (AE) and Serious adverse event (SAE) are defined as events that are reported after the signing the inform consent form (ICF).

Treatment-emergent adverse events (TEAEs) are defined as events that are newly reported after the first study drug treatment or are reported to have worsened in severity after the first study drug treatment. In the case where it is impossible to define an AE as treatment-emergent or not, the AE will be classified by the worst case assigned, i.e. a TEAE.

In section 24 Appendix 2 the algorithm is given for calculation of partial date imputation for adverse events (AEs) and it will be used for partially missing adverse event start and end date imputation.

Each adverse event will be described by following in listing:

- Subject Number
- Description (AE term) i.e. System organ class/ Preferred terms / Reported terms
- Duration (start and end dates)
- Severity of event
- Relationship to the investigational product
- Relationship to non-study drug treatment
- Relationship to the study procedure
- Action taken with the study treatment
- Outcome
- Whether SAE or not

Each serious adverse event will be described by following in listing:

Subject Number

CONFIDENTIAL CS.BS.01.00 TPL-1.0: Statistical Analysis Plan Template Page 41 of 85

- Description (SAE term) i.e. System organ class/ Preferred terms / Reported terms
- Duration (start and end dates)
- Seriousness criteria
- Toxicity grade
- Severity
- Causality
- Outcome

The following parameters will be summarised for the subject's adverse events as mentioned in eCRF

- Number of participants with at least one TEAEs
- Number of participants with at least one drug related TEAEs
- Number of participants with at least one serious TEAEs
- Number of participants with at least one drug related serious TEAEs
- TEAE by Severity
- TEAEs leading to Death
- Drug-related TEAEs leading to Death
- TEAEs leading to early withdrawn of study
- Injection site Adverse events

Derivations:

- If adverse event start date ≥ Study drug administration start date, then we will consider it as TEAE.
- If adverse event start date ≥ Study drug administration start date and adverse event related to study treatment = "YES", then we will consider it as drug related TEAEs.

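### Protocol 9.2 defines a reasonable possibility of relatedness as existing causation, against the plan's own possibility wording; read literally, it would lower the drug-related counts

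*Protocol*

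**What the plan says.** Protocol 9.2 has the investigator judge "whether or not an AE has a reasonable possibility of being related to study treatment, study device, or a study procedure", weighing the disease, other treatment and other pathology. The next sentence explains the term: a reasonable possibility "means that there is a cause and effect relationship between the investigational product, study device, and/or study procedure and the AE". The scale is binary: "The investigator answers yes or no when making this assessment". Slightly earlier, the same section says: "Investigators should record their assessment of the potential relatedness of each AE to protocol procedure and investigational product in the eCRFs".

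The answer, or the same judgement, is used in several places:

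- **Protocol 10.3.2.4:** "The proportion of subjects experiencing each TEAE that is assessed as possibly related to the study disease, drug, or procedures will also be summarized".
- **SAP 16.1:** if an event starts on or after the first dose and its relation to study treatment is YES, "then we will consider it as drug related TEAEs". The derivations of drug-related serious TEAEs and drug-related TEAEs leading to death carry the same YES condition.
- **Protocol 9.2.1.1:** SUSARs are serious events not listed in the Investigator's Brochure and "that the investigator identifies as related to investigational product or procedure".
- **Protocol 9.2.1:** an SAE before the first dose, or one learned of after the subject has left the study, triggers notification when it is considered *reasonably possibly related*.

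**The concern.** The question put to the investigator sets a possibility standard. The sentence that defines its key term sets a standard of existing causation, with no *may*, *possible* or *potential*. With only YES and NO available, a plausible but unproven event has no middle category. It is NO under the definition and YES under the question. Two sites can code the same event differently and both be following the protocol.

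This matters because the study is single-arm and its stated purpose is safety. With no comparator, the drug-related tables are the SAP's only tabulated attribution of adverse events to Basaglar. A reader of the analysis that Protocol 10.3.2.4 describes as possibly related would expect it to hold every event with a plausible link. Where the definition was followed, it would hold only events judged to be caused by the product.

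**Working it through.** No sample size, error rate or event count is involved, so the check compares the wording and then traces where the answer goes.

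**Step 1: the standards side by side.**

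| Place | Standard |
|---|---|
| Protocol 9.2, question to the investigator | possibility |
| Protocol 9.2, recording instruction | *potential* relatedness |
| Protocol 9.2, definition of the term | a causal relationship exists |
| Protocol 9.2.1, pre-dose and post-study SAEs | *reasonably possibly* related |
| Protocol 10.3.2.4, analysis | *possibly* related |

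Four of the five use a possibility standard. The definition is the exception, and it is the only explanation of the term in either document. It is current text: the amendment (b) summary in Appendix 7 lists no change to it.

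**Step 2: outputs that depend on the answer.** The three drug-related derivations in SAP 16.1 require YES, and no sponsor causality assessment enters them. SUSAR status in Protocol 9.2.1.1 rests on the investigator's judgement. The pre-dose and post-study triggers in 9.2.1 use similar words but do not refer to the yes/no field. They are exposed only if the investigator carries the 9.2 definition over to them.

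**Step 3: outputs that do not depend on it.** Protocol 9.2.1 requires notification of any SAE within 24 hours. It also has SAEs up to the last visit collected whatever the investigator thinks of causation. The all-cause TEAE and SAE summaries (SAP 16.2 and 20.2.1) do not use the answer. The primary endpoint (SAP 19.1.1) is derived from glucose values, symptoms and dates.

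**Step 4: direction and size.** Let R be the number of subjects with at least one TEAE that meets the possibility standard for a relation to the drug. Let q be the share of them for whom every such event is answered NO because causation is not established. Then

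count shown = (1 − q) × R.

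- q = 0 (investigators answer the question as put): (1 − 0) × R = R, no change.
- q = 0.5 (assumed, for scale only): (1 − 0.5) × R = R/2.
- q near 1 (definition applied strictly to everyone): the count approaches 0.

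The documents give neither R nor q. A literal reading can only lower the count, but by how much cannot be derived.

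**The case against.** The strongest reply is that investigators answer the question, not the gloss. The question says reasonable possibility, the recording instruction says potential relatedness, and no passage requires causation to be proven. Investigators may well apply the looser standard. The eCRF guidance and training materials are not in the documents, so how sites were instructed is unknown. This stands: a reader might infer that drug-related events *are* under-counted, but the documents show only that they would be where the definition is taken literally.

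Two further inferences go too far.

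- **That a single NO removes an event from SUSAR reporting.** Protocol 9.2.1.1 does rest on the investigator's view. But the sponsor receives every on-study SAE, has its own SUSAR procedures (not reproduced in the documents) and reviews aggregate safety data under 9.4.6. Loss of the event is possible but not established.
- **That the yes/no answer is the only attribution recorded anywhere.** Protocol 9.2.1 also has the investigator note each SAE's relationship to the drug for the narrative. The SAP 16.1 listings show relationship for every AE and causality for every SAE, so an event answered NO stays visible there.

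None of this removes the conflict or protects the drug-related tables. Nor can the analysis repair it, because a recorded NO does not show which standard was used. For an SAE learned of after the study, the investigator's judgement of possible relation decides whether Protocol 9.2.1 requires the sponsor to be told.

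**Conclusion.** The definition in Protocol 9.2 is wrong as written. It contradicts the question it is meant to explain and the possibility wording in 9.2, 9.2.1 and 10.3.2.4. Applied literally, it lowers the counts of drug-related, drug-related serious and drug-related fatal TEAEs. It could also affect SUSAR classification and the notification of pre-dose and post-study SAEs.

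The conclusion on direction assumes literal application at some sites. The size is unknown and may be zero. A numerical estimate would need an adverse event rate and a misclassification share, and the documents supply neither. A reader might also infer that the study's safety results as a whole are biased. They are not on this ground: the primary hypoglycemia endpoint, total TEAEs, total SAEs and 24-hour notification of on-study SAEs do not depend on the relatedness answer.

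**What to change.** In Protocol 9.2, state that a reasonable possibility means there is a *possible (potential)* cause-and-effect relationship between the product, device or procedure and the event. Use that one standard in 9.2.1, 9.2.1.1, 10.3.2.4, the eCRF guidance, site training and SAP 16.1.

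If events have already been assessed under the current wording, have sites re-confirm **all** relatedness answers, YES and NO, against the corrected definition. Re-opening only the NO answers could move the counts in one direction only, in an open-label study.

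The text change is one word and a training note. Re-confirmation adds site work only if assessments already exist. Reported drug-related percentages may be higher as a result.

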### **9.2.1. Serious Adverse Events**

An SAE is any AE from this study that results in 1 of the following outcomes:

- death
- initial or prolonged insubject hospitalization
- a life-threatening experience (that is, immediate risk of dying)
- persistent or significant disability/incapacity
- congenital anomaly/birth defect
- important medical events that may not be immediately life-threatening or result in death or hospitalization, but may jeopardize the subject or may require intervention to prevent 1 of the other outcomes listed in the definition above. Examples of such medical events include allergic bronchospasm requiring intensive treatment in an emergency department or at home, blood dyscrasias or convulsions that do not result in insubject hospitalization, or the development of drug dependency or drug abuse.
- severe hypoglycemia

If the investigator believes that a reported SAE of hypoglycemia does not meet any of the specific criteria outlined above, the investigator should select the outcome of “considered significant by the investigator for any other reason” in the eCRF.

All AEs occurring after signing the ICF are recorded in the eCRF and assessed for serious criteria. The SAE reporting to the sponsor begins after the subject has signed the ICF and has received investigational product. However, if an SAE occurs after signing the ICF, but prior to receiving investigational product, the SAE should be reported to the sponsor according to the SAE-reporting requirements and timelines (see Section 9.2) if it is considered reasonably possibly related to study procedure.

Study-site personnel must alert Lilly or its designee of any SAE within 24 hours of investigator awareness of the event via a sponsor-approved method. If alerts are issued via telephone, they are to be immediately followed with official notification on study-specific SAE forms. This 24-hour notification requirement refers to the initial SAE information and all follow-up SAE information. Subjects with a serious hepatic AE should have additional data collected using eCRFs ([Appendix 4](#)).

Pregnancy does not meet the definition of an AE. However, to fulfill regulatory requirements, any pregnancy should be reported following the SAE process to collect data on the outcome for both mother and fetus.

Investigators are not obligated to actively seek AEs or SAEs in subjects after they have discontinued (ET visit) and/or completed the study (follow-up visit), that is, the subject disposition eCRF has been completed. However, if the investigator learns of any SAE, including a death, at any time after a subject has been discharged from the study, and he/she considers the event reasonably possibly related to the study treatment or study participation, the investigator must promptly notify Lilly.

Serious AEs occurring up to and including the subject’s last study visit (or ET visit) will be collected, regardless of the investigator’s opinion of causation, in the clinical data collection database and the pharmacovigilance system at the sponsor. The investigator will make a note of the relationship of the event with the drug. This information will be included in the narrative.

### **9.2.1.1. Suspected Unexpected Serious Adverse Reactions**

Suspected unexpected serious adverse reactions (SUSARs) are serious events that are not listed in the Investigator’s Brochure (IB) and that the investigator identifies as related to investigational product or procedure. United States 21 CFR 312.32 and European Union Clinical Trial Directive 2001/20/EC, and the associated detailed guidance or national regulatory requirements in participating countries require the reporting of SUSARs. Lilly has procedures that will be followed for the identification, recording, and expedited reporting of SUSARs that are consistent with global regulations and the associated detailed guidance.

### **9.2.2. Adverse Event Monitoring with a Systematic Questionnaire**

Not applicable.

### **9.2.3. Complaint Handling**

Lilly collects product complaints on investigational products and drug delivery systems used in clinical studies in order to

- ensure the safety of study participants
- monitor quality, and
- facilitate process and product improvements.

Subjects will be instructed to contact the investigator as soon as possible if he or she has a complaint or problem with the investigational product or glucometer so that the situation can be assessed. A replacement instrument may be used as long as the procedures and the subsequent visits continue to fall within the allowable time frames.

The investigator or his or her designee is responsible for handling the following aspects of the product complaint process in accordance with the instructions provided for this study:

- recording a complete description of the product complaint reported and any associated AEs using the study-specific complaint forms provided for this purpose, and
- faxing the completed product complaint form within 24 hours to Lilly or its designee.

If the investigator is asked to return the product for investigation, he/she will return a copy of the product complaint form with the product.

### **9.3. Treatment of Overdose**

Refer to Section 6.2.2.9 of the IB for information on management of insulin overdose.

## **9.4. Safety**

### **9.4.1. *Electrocardiograms***

For each subject, 12-lead electrocardiograms (ECGs) should be collected according to the Schedule of Activities (Section 2).

Any clinically significant findings from ECGs that result in a diagnosis and that occur after the subject receives the first dose of the investigational product should be reported to Lilly or its designee as an AE via eCRF/electronic data entry/designated data transmission methods.

### **9.4.2. *Vital Signs***

For each subject, vital signs measurements will be conducted as mentioned in the Schedule of Activities (Section 2).

Any clinically significant findings from vital signs measurement that result in a diagnosis and that occur after the subject receives the first dose of study treatment should be reported to Lilly or its designee as an AE via eCRFs.

### **9.4.3. *Laboratory Tests***

For each subject, laboratory tests detailed in ([Appendix 2](#)) will be conducted according to the Schedule of Activities (Section 2).

Lilly or its designee will provide the investigator with the results of laboratory tests analyzed by a central vendor.

Any clinically significant findings from laboratory tests that result in a diagnosis, and that occur after the subject receives the first dose of investigational product should be reported to Lilly or its designee as an AE via eCRFs.

### **9.4.4. *Immunogenicity Assessments***

Not applicable.

### **9.4.5. *Other Tests***

Not applicable.

### **9.4.6. *Safety Monitoring***

Lilly will periodically review evolving aggregate safety data within the study by appropriate methods.

#### **9.4.6.1. *Hepatic Safety Monitoring***

If a study subject experiences elevated ALT  $\geq 3X$  ULN, ALP  $\geq 2X$  ULN, or elevated TBL  $\geq 2X$  ULN, liver testing ([Appendix 4](#)) should be repeated within 3 to 5 days, including

- ALT
- AST
- ALP
- TBL
- direct bilirubin
- gamma-glutamyl transferase, and
- creatine kinase.

These tests are performed to confirm the abnormality and to determine if the levels are increasing or decreasing. If the abnormality persists or worsens, clinical and laboratory monitoring should be initiated by the investigator and in consultation with the study medical monitor. Monitoring of ALT, AST, TBL, and ALP should continue until levels normalize or return to approximate screening visit (Week -2) levels.

#### **Hepatic Safety Data Collection**

Additional safety data as mentioned in [Appendix 4](#) should be collected via the eCRF if 1 or more of the following conditions occur:

- elevation of serum ALT to  $\geq 5X$  ULN on 2 or more consecutive blood tests
- elevated serum TBL to  $\geq 2X$  ULN (except for cases of known Gilbert's syndrome)

- elevation of serum ALP to  $\geq 2X$  ULN on 2 or more consecutive blood tests
- subject discontinued from treatment due to a hepatic event or abnormality of liver tests, and/or
- hepatic event considered to be a SAE.

